#### **7.4.4 Criteria to Resume Treatment (BMS-986205 and Nivolumab)**

Participants may resume treatment with study treatments when the drug-related AE(s) resolve to Grade  $\leq$  1 or baseline value, with the following exceptions:

- Participants may resume treatment in the presence of Grade 2 fatigue.
- Participants who have not experienced a Grade 3 drug-related skin AE may resume treatment in the presence of Grade 2 skin toxicity.
- For participants with Grade 2 AST, ALT and/or Total Bilirubin abnormalities, dosing may resume when laboratory values return to baseline and management with corticosteroids, if needed, is complete.
- Participants with combined AST/ALT AND total bilirubin values meeting discontinuation parameters ([Section 8.1.1](#)) should have treatment permanently discontinued.
- Drug-related pulmonary toxicity, diarrhea or colitis must have resolved to baseline before treatment is resumed. Participants with persistent Grade 1 pneumonitis after completion of a steroid taper over at least 1 month may be eligible for retreatment if discussed with and approved by BMS Medical Monitor/designee.

Participants with drug-related endocrinopathies adequately controlled with only physiologic hormone replacement may resume treatment after consultation with the BMS Medical Monitor/designee. Adrenal insufficiency requires discontinuation regardless of control with hormone replacement.

For participants who have BMS-986205 held for elevations of methemoglobin, dosing may resume when the methemoglobin levels have decreased to below the institutional ULN and any associated AEs have resolved to Grade  $\leq$  1 or baseline value. Dose modification of BMS-986205 should be considered when resuming after a delay (see [Section 7.4.2](#)).

[REDACTED]

#### **7.4.6 Detection of Methemoglobinemia**

BMS-986205 may produce a p-chloroaniline metabolite. P-chloroaniline has been associated with the production of methemoglobin. Symptoms of methemoglobinemia are related to the lack of oxygen delivery to tissues and are proportional to the fraction of methemoglobin, as described below for participants with normal hemoglobin levels.

Symptoms associated with elevations of methemoglobin are as follows:

- 0% to 10% - Usually asymptomatic
- 10% to 20% - Cyanosis without other symptoms
- 20% to 50% - Headache, dyspnea, lightheadedness (possibly syncope), weakness, confusion, palpitations, chest pain
- 50% to 70% - Coma, seizures, arrhythmias; acidosis
- > 70% - Usually death

Note that participants with anemia may experience symptoms at lower methemoglobin percentages than listed above, depending on the degree of anemia.

Increasing levels of methemoglobin may confound the results of standard pulse oximeters, with values of around 85% reported consistently as methemoglobin levels increase, regardless of the true oxygen saturation.

When methemoglobinemia is suspected, part of the diagnostic work-up includes evaluation for other disorders that can present with a similar clinical picture, including cardiac and pulmonary disease. A fresh peripheral blood sample (either venous or arterial) should be sent for evaluation of methemoglobin levels; methemoglobin levels may vary with storage of blood.

In this study methemoglobin testing will be performed at screening, at each cycle (for BMS-986205 treated participants only), and as clinically indicated. For management of methemoglobinemia, see [Section 7.7.4](#).

#### **7.5 Preparation/Handling/Storage/Accountability**

For nivolumab, refer to the current version of the IB and/or Pharmacy Manual for complete storage, handling, dispensing, and infusion information.

Similarly, for BMS-986205, refer to the current version of the IB and/or Pharmacy Manual for complete storage, handling, and dispensing information.

The investigational products should be stored in a secure area according to local regulations. It is the responsibility of the investigator to ensure that investigational products are only dispensed to

study participants. The investigational products must be dispensed only from official study sites by authorized personnel according to local regulations.

The product storage manager should ensure that the study treatments are stored in accordance with the environmental conditions (temperature, light, and humidity) as determined by BMS. If concerns regarding the quality or appearance of the study treatments arise, do not dispense the study treatment and contact BMS immediately.

Study treatment not supplied by BMS will be stored in accordance with the package insert.

Investigational product documentation (whether supplied by BMS or not) must be maintained that includes all processes required to ensure drug is accurately administered. This includes documentation of drug storage, administration and, as applicable, storage temperatures, reconstitution, and use of required processes (eg, required diluents, administration sets).

Further guidance and information for final disposition of unused study treatments are provided in [Appendix 2](#).

### **7.5.1 Retained Samples for Bioavailability / Bioequivalence**

Not applicable.

### **7.6 Treatment Compliance**

Treatment compliance of nivolumab will be monitored by drug accountability as well as the participant's medical record and eCRF.

Treatment compliance of BMS-986205 will be monitored by drug accountability, as well as by recording BMS-986205 administration in the participant pill diary (as applicable), medical record, and eCRF. Participants should bring all drug containers to each study visit for drug reconciliation. The pill diary should be reviewed at each clinic visit and submitted at the end of each cycle, as applicable.

[REDACTED]

[REDACTED]

[REDACTED]

[REDACTED]

[Redacted text block containing multiple paragraphs of blacked-out content]

[Redacted]

[Redacted]

[Redacted]

[Redacted]

[Redacted]

[REDACTED]

[REDACTED]

[REDACTED]

[REDACTED]

[Redacted text block]

[Redacted text block]

[Redacted text block]

[Redacted text block]

[Redacted text block]

[Redacted text block]

[Redacted text block]

[Redacted text block]

[Redacted text block]

[REDACTED]

[REDACTED]

[REDACTED]

[REDACTED]

## **7.8 Treatment After the End of the Study**

At the conclusion of the study, participants who continue to demonstrate clinical benefit will be eligible to receive BMS-supplied study treatment for the maximum treatment duration specified in [Section 7.1](#). Study treatment will be provided via an extension of the study, a rollover study requiring approval by responsible health authority and ethics committee, or through another mechanism at the discretion of BMS. See [Section 5.4.2](#) for more information.

BMS reserves the right to terminate access to BMS supplied study treatment if any of the following occur: a) the study is terminated due to safety concerns; b) the development of BMS-986205 is terminated for other reasons, including but not limited to lack of efficacy and/or not meeting the study objectives; c) the participant can obtain medication from a government-sponsored or private health program. In all cases BMS will follow local regulations.

## **8 DISCONTINUATION CRITERIA**

### **8.1 Discontinuation from Study Treatment**

Participants **MUST** discontinue investigational product (and non-investigational product at the discretion of the investigator) for any of the following reasons:

- Participant's request to stop study treatment. Withdrawal of consent/assent may be requested by participants, parents, guardians, or legally acceptable representatives, in accordance with

local regulations. The wishes of minor participants to withdraw their assent should also be respected. Participants who request to discontinue study treatment will remain in the study and must continue to be followed for protocol specified follow-up procedures. The only exception to this is when a participant specifically withdraws consent for any further contact with him/her or persons previously authorized by the participant to provide this information.

- Any clinical AE, laboratory abnormality or intercurrent illness which, in the opinion of the investigator, indicates that continued participation in the study is not in the best interest of the participant
- Termination of the study by BMS
- Loss of ability to freely provide consent through imprisonment or involuntarily incarceration for treatment of either a psychiatric or physical (eg, infectious disease) illness
- Additional protocol-specified reasons for discontinuation ([Section 8.1.1](#))
- Documented investigator-assessed progression as defined by RECIST v1.1 (see [Appendix 12](#)) unless participant meets criteria for treatment beyond progression

In the case of pregnancy, the investigator must immediately notify the Sponsor or designee of this event. In most cases, the study treatment will be permanently discontinued in an appropriate manner (eg, dose tapering if necessary for participant safety). Please contact the Sponsor or designee within 24 hours of awareness of the pregnancy. If the investigator determines a possible favorable benefit/risk ratio that warrants continuation of study treatment, a discussion between the investigator and the Sponsor or designee must occur.

Refer to the Schedule of Activities for data to be collected at the time of treatment discontinuation and follow-up and for any further evaluations that can be completed.

All participants who discontinue study treatment should comply with protocol specified follow-up procedures as outlined in [Section 2](#). The only exception to this requirement is when a participant withdraws consent for all study procedures including post-treatment study follow-up or loses the ability to consent freely (ie, is imprisoned or involuntarily incarcerated for the treatment of either a psychiatric or physical illness).

The assessment for discontinuation of nivolumab should be made separately from the assessment made for discontinuation of BMS-986205. Although there is overlap among the discontinuation criteria, if discontinuation criteria are met for BMS-986205 but not for nivolumab, treatment with nivolumab may continue if BMS-986205 is discontinued. If a participant discontinues nivolumab, they must also discontinue BMS-986205.

If a participant receiving nivolumab/BMS-986205 combination meets criteria for discontinuation and investigator is unable to determine whether the event is related to both or one study drug, the participant should discontinue both nivolumab and BMS-986205 and be taken off the treatment phase of the study.

If study treatment is discontinued prior to the participant's completion of the study, the reason for the discontinuation must be documented in the participant's medical records and entered on the appropriate eCRF page.

### **8.1.1 BMS-986205 and Nivolumab Dose Discontinuation**

BMS-986205 and nivolumab treatment should be permanently discontinued for the following:

- Any occurrence of serotonin syndrome
- Any Grade 2 drug-related uveitis, eye pain or blurred vision that does not respond to topical therapy and does not improve to Grade 1 severity within the time frame permitted for dose delays OR requires systemic treatment
- Any event requiring more than 1 dose reduction of BMS-986205 (see [Section 7.4.2](#)), except for those related to methemoglobinemia or QTc prolongations, which require only discontinuation of BMS-986205 alone; subjects may continue to receive nivolumab in these situations (see also [Section 8.1.2](#))
- Any drug-related event requiring 10 mg per day or greater prednisone or equivalent for more than 12 weeks, except for adrenal replacement steroid dose >10mg.
- Immune-mediated encephalitis of any grade
- Any Grade 3 non-skin, drug-related AE lasting > 7 days, or recurs with the following exceptions for laboratory abnormalities, diarrhea, colitis, neurologic toxicity, drug-related uveitis, pneumonitis, bronchospasm, hypersensitivity reactions, infusion reactions, and endocrinopathies:
  - Grade 3 drug-related diarrhea, colitis, neurologic toxicity, uveitis, pneumonitis, bronchospasm, myocarditis, hypersensitivity reaction, or infusion reaction of any duration requires discontinuation
  - Grade 3 drug-related endocrinopathies, adequately controlled with only physiologic hormone replacement do not require discontinuation. Adrenal insufficiency requires discontinuation regardless of control with hormone replacement.
  - Grade 3 drug-related laboratory abnormalities do not require treatment discontinuation except:
    - ◆ Grade 3 drug-related thrombocytopenia > 7 days or associated with bleeding requires discontinuation
    - ◆ Any drug-related liver function test (LFT) abnormality that meets the following criteria require discontinuation:
      - Grade  $\geq 3$  drug-related AST, ALT or Total Bilirubin requires discontinuation\*
      - Concurrent AST or ALT > 3 x ULN and total bilirubin > 2x ULN
- \* In most cases of Grade 3 AST or ALT elevation, study treatment(s) will be permanently discontinued. If the investigator determines a possible favorable benefit/risk ratio that warrants continuation of study treatment(s), a discussion between the investigator and the BMS Medical Monitor/designee must occur.
- Any Grade 4 drug-related AE or laboratory abnormality (including but not limited to creatinine, AST, ALT, or Total Bilirubin), except for the following events which do not require discontinuation:
  - Grade 4 neutropenia  $\leq 7$  days
  - Grade 4 lymphopenia or leukopenia or asymptomatic amylase or lipase

- Isolated Grade 4 electrolyte imbalances/abnormalities that are not associated with clinical sequelae and are corrected with supplementation/appropriate management within 3 calendar days of their onset
- Grade 4 drug-related endocrinopathy AEs, such as, hyper- or hypothyroidism, or glucose intolerance, which resolve or are adequately controlled with physiologic hormone replacement (corticosteroids, thyroid hormones) or glucose-controlling agents, respectively, may not require discontinuation after discussion with and approval from the BMS Medical Monitor/designee.
- Any AE, laboratory abnormality, or intercurrent illness which, in the judgment of the investigator, presents a substantial clinical risk to the participant with continued BMS-986205 and nivolumab dosing
- Any event that leads to delay in dosing of nivolumab lasting > 10 weeks from the previous dose requires discontinuation, with the following exceptions:
  - Dosing delays to allow for prolonged steroid tapers to manage drug-related AEs are allowed.
  - Dosing delays lasting > 10 weeks from the previous dose that occur for non-drug-related reasons may be allowed if approved by the BMS Medical Monitor/designee.
- Any event requiring 10 mg per day or greater prednisone or equivalent for more than 12 weeks except for adrenal replacement steroid dose >10mg

Prior to re-initiating treatment in a participant with a dosing delay lasting > 10 weeks, the BMS Medical Monitor/designee must be consulted. Tumor assessments should continue as per protocol even if dosing is delayed. Periodic study visits to assess safety and laboratory studies should also continue every 4 weeks or more frequently if clinically indicated during such dosing delays.

[figure not shown]
Participants who are discontinued from nivolumab, must also discontinue BMS-986205.

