#### **7.4.2 BMS-986205 Dose Modifications**

A dose reduction of BMS-986205 is defined as a change from a 100 mg QD tablet to a 50 mg QD tablet.

Doses of BMS-986205 should be reduced for the following AEs attributable to study therapy that do not otherwise meet criteria for discontinuation:

- Grade 3 fatigue, nausea, vomiting, or anemia related to study treatment
- Methemoglobin  $\geq 15\%$
- Clinically significant elevations in methemoglobin (generally 10%, with a normal hemoglobin level) with any associated Grade 3 AE (hypoxia, dyspnea, confusion, etc.) attributable to sustained elevations of methemoglobin and not attributable to another etiology
- QTcF > 500 msec confirmed by at least 1 repeat ECG and at least 60 msec above baseline (See [Appendix 9](#))

Dose modification and interruption of BMS-986205 may occur in the setting of lower grade AEs and/or be more conservative than indicated above based on the clinical judgment of the investigator and in consultation with the BMS Medical Monitor/designee. For an AE requiring dose modification, BMS-986205 should be delayed to allow improvement of the AE, even if the AE does not otherwise meet criteria for dose delay ([Section 7.4.3](#)).

Re-escalation of BMS-986205 will not be permitted once the dose of BMS-986205 has been reduced for a participant.

Only one dose reduction is permitted. The participant must discontinue study treatments if a subsequent dose reduction of BMS-986205 is required (see [Section 8.1.1](#)).

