#### **7.4.3 Dose Delay (BMS-986205 and Nivolumab)**

BMS-986205 and nivolumab administration should be delayed for the following:

- Grade 2 non-skin, drug-related AE, with the exception of fatigue, nausea, vomiting and anemia
- Grade 2 drug-related creatinine, AST, ALT and/or Total Bilirubin abnormalities
- Grade 3 skin, drug-related AE
- Grade 3 drug-related fatigue, nausea, vomiting, and anemia
- Grade 3 drug-related laboratory abnormality, with the following exceptions:
  - Grade 3 lymphopenia or asymptomatic amylase or lipase elevations do not require dose delay
  - Grade  $\geq 3$  AST, ALT, Total Bilirubin will require dose discontinuation (see [Section 8.1.1](#))
- Any AE, laboratory abnormality, or intercurrent illness which, in the judgment of the investigator, warrants delaying the dose of study medication

In addition, **only BMS-986205** should be delayed for the following:

- Methemoglobin  $\geq 15\%$
- Clinically significant elevations in methemoglobin (generally 10% with a normal hemoglobin level) with any associated Grade 3 AE (hypoxia, dyspnea, confusion, etc.) attributable to sustained elevations of methemoglobin and not attributable to another etiology
- QTcF  $> 500$  msec confirmed by at least 1 repeat ECG and at least 60 msec above baseline (See [Appendix 9](#))

[Appendix 14](#) presents the above criteria in tabular format.

If nivolumab dosing is delayed for reasons other than study drug toxicity (eg, administrative issues, holidays, etc), BMS-986205 dosing should continue uninterrupted.

Participants may continue to receive nivolumab during dose delays of BMS-986205 for elevations of methemoglobin and associated events, as well as QTcF prolongations.

For participants with methemoglobin elevations with associated Grade 3 AEs, if contribution of nivolumab to the associated AE cannot be ruled out (eg, a participant with dyspnea in whom pneumonitis has not yet been ruled out), nivolumab dosing should be delayed as well. See [Section 7.7.4](#) for management of methemoglobinemia.

If BMS-986205 dosing is delayed, dose reduction may be necessary. See [Section 7.4.2](#).

If dosing is resumed after a delay, BMS-986205 may be resumed as soon as the criteria to resume treatment are met (see [Section 7.4.4](#)). Nivolumab should be resumed as soon as possible after criteria to resume treatment are met, but may be resumed later than BMS-986205 given the differences in each drug's administration.

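### Protocol 8.1.1 gives two outcomes for nivolumab when a methemoglobin-attributed Grade 3 event recurs at 50 mg, and 8.1.2 disagrees with 8.1.1 and 7.4.2 on a second dose reduction for other events

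*Protocol*

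**What the plan says.** Protocol 7.4.2 allows one reduction of BMS-986205, from 100 mg to 50 mg daily. Its opening condition reads: "Doses of BMS-986205 should be reduced for the following AEs attributable to study therapy that do not otherwise meet criteria for discontinuation". One trigger is a clinically significant methemoglobin elevation "with any associated Grade 3 AE (hypoxia, dyspnea, confusion, etc.) attributable to sustained elevations of methemoglobin and not attributable to another etiology". Grade 3 fatigue, nausea, vomiting or anemia is another. The last paragraph of 7.4.2 adds "The participant must discontinue study treatments if a subsequent dose reduction of BMS-986205 is required" and points to 8.1.1.

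Protocol 8.1.1 lists events for which both drugs stop permanently. Two of its bullets matter here:

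- The dose-reduction bullet covers any event that would need more than one reduction of BMS-986205, "except for those related to methemoglobinemia or QTc prolongations, which require only discontinuation of BMS-986205 alone". It says that nivolumab may then go on, and refers the reader to 8.1.2.
- The Grade 3 bullet covers "Any Grade 3 non-skin, drug-related AE lasting > 7 days, or recurs with the following exceptions". The exceptions are laboratory abnormalities and a set of named conditions, some of which are stricter than the main rule ("Grade 3 drug-related diarrhea, colitis, neurologic toxicity, uveitis, pneumonitis, bronchospasm, myocarditis, hypersensitivity reaction, or infusion reaction of any duration requires discontinuation"). Clinical events caused by methemoglobin are not among them.

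Protocol 8.1.2 lists events that stop BMS-986205 only. Its lead-in lets nivolumab go on unless something else calls for its delay or discontinuation. Its first bullet covers any event needing more than one reduction, with no restriction to methemoglobinemia or QTc.

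Two other places bear on the question. Protocol 8.1 asks for the drugs to be assessed separately: "if discontinuation criteria are met for BMS-986205 but not for nivolumab, treatment with nivolumab may continue if BMS-986205 is discontinued". It stops both when the investigator cannot tell whether one or both drugs are responsible. Protocol 7.4.3, on delays, says: "Participants may continue to receive nivolumab during dose delays of BMS-986205 for elevations of methemoglobin and associated events, as well as QTcF prolongations".

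**The concern.** Two bullets of the same list apply to the same event and send nivolumab in opposite directions. A site facing a methemoglobin-attributed Grade 3 dyspnea or hypoxia that returns at 50 mg must stop BMS-986205 on any reading. Whether the participant also permanently loses nivolumab, for an event attributed to the other drug, depends on which bullet is followed. Section 9 rules out waivers, so a site that takes the Grade 3 bullet literally has no evident freedom to depart from it.

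A second mismatch sits next to the first. For a second reduction needed for some other reason, 8.1.1 and 7.4.2 say stop both, while 8.1.2 says stop BMS-986205 only.

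**Working it through.** The check is mainly a comparison of text; a short count follows for scale.

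**Case 1: Grade 3 dyspnea or hypoxia attributed to methemoglobin, reduced to 50 mg, recurs**

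| Text | Outcome for BMS-986205 | Outcome for nivolumab |
|---|---|---|
| 8.1.1, dose-reduction bullet | stop | may continue (methemoglobin exemption) |
| 8.1.1, Grade 3 bullet | stop | stop (Grade 3, non-skin, drug-related, recurrent, not excepted) |

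The laboratory exception inside the Grade 3 bullet does not help. It covers a raised methemoglobin value, not a clinical event such as dyspnea.

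Does other text settle it?

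- 8.1, separate assessment: nivolumab may continue if its own criteria are not met. Read literally, the Grade 3 bullet says they are met, so this leans toward sparing nivolumab without deciding.
- 8.1, attribution: both drugs stop when the cause cannot be assigned. That an event assigned to BMS-986205 alone stops only that drug is a fair inference, but it is not written.
- 8.1.2, lead-in: nivolumab stops only if something else requires it, and the recurring event is arguably not something else. But the lead-in refers back to 8.1.1, where the two bullets sit.
- 7.4.3: same logic in favor of nivolumab, but for delays, not permanent discontinuation.
- 7.4.2, opening condition: can be read the other way, as putting the discontinuation criteria first. It decides between reducing and stopping BMS-986205 and does not address nivolumab. It is a weak counterweight.

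Most of this favors continuing nivolumab. None of it names the two bullets or says which governs.

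**Case 2: Grade 3 fatigue, reduced to 50 mg, recurs**

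| Text | Outcome for nivolumab |
|---|---|
| 8.1.1, dose-reduction bullet | stop (not methemoglobinemia or QTc) |
| 7.4.2, last paragraph | stop (plural treatments, pointing to 8.1.1) |
| 8.1.2, first bullet | may continue |

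Here the texts disagree directly.

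**Maximum at stake for one participant in case 1**

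Inputs: enrollment closed 19-Apr-2018 (Synopsis); first dose within 3 days of randomization (Table 2-2); treatment up to 104 weeks; nivolumab every 4 weeks, with 25 to 31 days between doses (7.1.2); current revision dated 25-Oct-2018 (Document History).

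- Latest first dose: 19-Apr-2018 + 3 days = 22-Apr-2018 (day 0). Then 25-Oct-2018 is day 186, and treatment ends at 104 × 7 = day 728.
- With spacing s, infusions fall on days s·k below 728. Count those on or after day 186.
- s = 28: days 0 to 700, 26 infusions in all. From day 196 (k = 7) to day 700 (k = 25): 25 − 7 + 1 = **19**.
- s = 28, with the day-168 infusion delayed 18 days to day 186: days 186 to 718, **20**.
- s = 31 throughout: days 186 (k = 6) to 713 (k = 23), **18**.
- s = 25 throughout: days 200 (k = 8) to 725 (k = 29), **22**.

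These counts assume the latest possible first dose, recurrence on the revision date, and treatment to week 104 with no progression or other stop. Earlier first doses, later recurrences or progression all lower them. For comparison, the protocol's retired sample-size section assumed a median PFS of 11.8 months for the combination, against 728 / 30.4375 = 23.9 months of maximum treatment.

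**The case against.** The best reply is that the protocol already answers case 1. The methemoglobin exemption is a specific, affirmative permission in the same list, and a specific rule normally prevails over a general one. Section 8.1 acknowledges that the criteria overlap and assesses the drugs separately. The 7.4.2 trigger presupposes that other causes have been excluded, so the rule for unattributable events is not engaged. Sections 8.1.2 and 7.4.3 run the same way. Investigators may in any case stop BMS-986205 and keep nivolumab at their discretion, and Section 9 has immediate safety concerns discussed with the sponsor. Sections 3.1.1 and 7.7.4 and Appendix 14 cannot be read in the public text and may settle the matter.

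Much of this stands. A reader might infer that nothing in the protocol bears on precedence, or that it orders nivolumab stopped; neither is supported, because the surrounding text mostly points to sparing it. What remains is that a site must construct this answer from several sections while one bullet, read alone, says the opposite. The reply also leaves case 2 untouched.

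A reader might also infer that methemoglobin-attributed confusion stops both drugs at first occurrence, as neurologic toxicity. The documents do not support this. They nowhere class such confusion as neurologic toxicity, and doing so would defeat its listing as a reduction trigger in 7.4.2.

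Finally, it can be said that aligning 8.1.2 with 8.1.1 is a clinical choice that could equally go the other way, and that it would take nivolumab from some participants. The choice is the sponsor's. However, 7.4.2, the 8.1.1 bullet and the pointer from its exemption to 8.1.2 all support the narrower scope.

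**Conclusion.** The point holds as a minor inconsistency. In case 1 a general bullet omits an exemption that a neighboring bullet grants, and the probable intent is to continue nivolumab. In case 2 the sections contradict each other.

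The reach of case 1 is narrow: Arm A, still on BMS-986205, a Grade 3 clinical event attributed to methemoglobin, one reduction taken, recurrence at 50 mg, and no nivolumab contribution. The number of such participants cannot be derived from the documents and may be zero. The 19 of 26 infusions (18 to 22 at the dosing-window limits) is a per-participant maximum under the assumptions listed, not an expected loss.

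A reader might infer that trial results are at risk. They are not: no efficacy analysis is planned, and the safety outputs are descriptive summaries and listings, so no planned analysis is affected. The conclusion is subject to the three unreadable sections, whose absence from the public text is not counted against the plan.

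**What to change.** By protocol revision:

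1. In the Grade 3 bullet of 8.1.1, add: *except AEs attributable to methemoglobin elevation and not to another etiology, which require discontinuation of BMS-986205 only; if a nivolumab contribution cannot be excluded, discontinue both.*
2. Limit the first bullet of 8.1.2 to methemoglobinemia and QTc events, and repeat that exemption in the last paragraph of 7.4.2, so that 7.4.2, 8.1.1 and 8.1.2 agree.
3. Check the result against Sections 3.1.1 and 7.7.4 and Appendix 14.

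The cost is a few lines of wording and IRB/IEC approval of the revision, as Appendix 2 requires. No extra data or procedures are needed. If the sponsor prefers nivolumab to continue after a second reduction for any event, 8.1.1 and 7.4.2 should be changed instead and the clinical reason given.

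### Protocol 8.1.1: for endocrinopathies lasting more than 7 days or recurring, the Grade 3 exception omits two routes that Grade 4 allows with approval

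*Protocol*

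**What the plan says.** Protocol Section 8.1.1 opens with "BMS-986205 and nivolumab treatment should be permanently discontinued for the following" and then lists triggers. Two of them govern endocrine events, and a third sentence, in Section 7.4.4, governs restart.

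- **Grade 3 (8.1.1).** The trigger is "Any Grade 3 non-skin, drug-related AE lasting > 7 days, or recurs with the following exceptions", and endocrinopathies are among the categories then named. Their sub-bullet reads "Grade 3 drug-related endocrinopathies, adequately controlled with only physiologic hormone replacement do not require discontinuation". Adrenal insufficiency has its own sentence and is not at issue here. A further sub-bullet says "Grade 3 drug-related laboratory abnormalities do not require treatment discontinuation except" for certain thrombocytopenia and liver-test findings.
- **Grade 4 (8.1.1).** Any Grade 4 drug-related event or laboratory abnormality is a trigger, whatever its duration. Among the exceptions are "Grade 4 drug-related endocrinopathy AEs, such as, hyper- or hypothyroidism, or glucose intolerance, which resolve or are adequately controlled with physiologic hormone replacement". The sentence goes on to add glucose-controlling agents as a separate means of control. It makes continuation possible, not automatic, after the Medical Monitor or designee has discussed and approved it.
- **Restart (7.4.4).** "Participants with drug-related endocrinopathies adequately controlled with only physiologic hormone replacement may resume treatment after consultation with the BMS Medical Monitor/designee". This sentence has no grade limit. The general rule in that section is recovery to Grade 1 or below, or to baseline.

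Section 8.1 makes the reasons in 8.1.1 mandatory, and Section 9 rules out protocol waivers and exemptions.

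**The concern.** The two exceptions do not use the same conditions. The Grade 3 sub-bullet accepts a single means of control and adds the word *only*. The Grade 4 bullet names hyperthyroidism and glucose intolerance and accepts resolution and glucose-controlling agents as well. For some events the lower grade is therefore permanently stopped where the higher grade may continue.

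Two things are at stake. A participant could permanently lose both drugs for an event that has resolved or is controlled. And sites that notice the inversion may settle it differently. Safety is all that the revised protocol still assesses. SAP Section 3.1.1 counts adverse events leading to discontinuation, SAP Section 7.5.3 lists them and SAP Section 7.3 lists study medication received, so those outputs would partly reflect how each site read the rule. The sentences bear on both arms, since both receive nivolumab.

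**Working it through.** No figure in the plan is involved, so the check is a comparison of clauses followed by applying them to cases.

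**Clause by clause (Protocol 8.1.1)**

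| Element | Grade 3 endocrinopathy | Grade 4 endocrinopathy | Narrower or stricter |
|---|---|---|---|
| Trigger | Lasts > 7 days, or recurs | Any duration | Grade 4 |
| Conditions that avoid a stop | One: hormone replacement only | Three: resolution, hormone replacement, glucose-controlling agents | Grade 3 |
| Approval needed for the exception | None stated | Medical Monitor discussion and approval | Grade 4 |
| Discussion route if the condition is not met | None stated | Not applicable to events that resolve or are controlled as above | Grade 3 |

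On the last row, 8.1.1 does give a discussion route for Grade 3 AST or ALT elevation, but none for Grade 3 endocrinopathies.

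**Applied to cases, read literally**

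1. *Hyperthyroidism, Grade 3 for 7 days or less, no recurrence.* The Grade 3 trigger is not met, so there is no stop. At Grade 4 the trigger is met at once and continuation needs approval.
2. *Hyperthyroidism, still Grade 3 on day 8, resolving on day 21 without hormone replacement.* The trigger is met from day 8 (> 7 days) and the sub-bullet's condition is not met, so both drugs stop permanently. At Grade 4 the event resolves and may continue with approval; that exception sets no time limit for resolution.
3. *Glucose intolerance, Grade 3 for more than 7 days or recurring, controlled with a non-hormonal agent.* The trigger is met and control is not by hormone replacement only, so both drugs stop permanently. At Grade 4 it may continue with approval.
4. *Hypothyroidism controlled with thyroid hormone.* At Grade 3 there is no stop and 8.1.1 asks for no approval. At Grade 4 approval is needed. Here Grade 3 is the more lenient.
5. *A glucose or thyroid value recorded only as a Grade 3 laboratory abnormality.* The laboratory exception can cover it, so there need be no stop.

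Cases 2 and 3 show the inversion; cases 1, 4 and 5 mark its limits.

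**How far case 5 reaches.** Section 9.2.7 expects the clinical term rather than the laboratory term wherever possible. Appendix 3 says abnormal tests are reported as adverse events only when no final diagnosis is available. A diagnosed hyperthyroidism or glucose intolerance would therefore normally be recorded as a clinical event, outside the laboratory exception.

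**Restart.** A Grade 4 glucose intolerance allowed to continue on a glucose-controlling agent does not fit the endocrinopathy sentence in 7.4.4, which accepts hormone replacement only. If dosing was held, the general restart rule is all that remains.

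**The case against.** The strongest reply is that the stop is inferred, not written. The Grade 3 lead-in names endocrinopathies among its exceptions, and where 8.1.1 wants a stop inside that list it says so, as for diarrhea, colitis and adrenal insufficiency. It nowhere says that a thyroid or glucose event controlled by other means must stop. This does not carry: if the lead-in alone exempted every endocrinopathy, the sub-bullet's condition on how the event is controlled would do nothing. Nor can hormone replacement simply be stretched to glucose treatment, because the Grade 4 bullet illustrates it with corticosteroids and thyroid hormones and lists glucose-controlling agents separately.

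Several other objections stand as limits on the point.

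- A reader might infer that any Grade 3 hyperthyroidism or glucose intolerance ends both drugs. The documents do not support that: the event must last more than 7 days or recur, and the laboratory exception may apply.
- A reader might infer that the Grade 3 rule is harsher overall. It is not; its trigger is narrower, and its exception needs no approval.
- Cases 2 and 3, where they rest on duration, assume that the event is still Grade 3 after day 7. The CTCAE grading text is not in the documents, so this cannot be settled from them. The recurrence limb does not need that assumption.
- Section 7.4.4 does not contradict 8.1.1. Being spared permanent discontinuation and not yet being eligible to restart are compatible.
- The affected SAP output on discontinuations is descriptive, with no test between arms, and different readings by sites are a risk rather than something shown.

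It can also be said that enrollment has closed. But treatment runs up to 104 weeks. A participant randomized as late as 19-Apr-2018 and dosed within 3 days could be treated until mid-April 2020 (104 × 7 = 728 days), nearly 18 months after Revised Protocol 02 of 25-Oct-2018. The wording still had work to do.

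**Conclusion.** The point holds in a limited form. For Grade 3 drug-related endocrinopathies that last more than 7 days or recur, the exception in 8.1.1 leaves out resolution and glucose-controlling agents, both of which the Grade 4 exception accepts subject to approval. The literal result is inverted for two kinds of event: hyperthyroidism that resolves without hormone replacement, and glucose intolerance controlled with a non-hormonal agent. The mismatch with 7.4.4 is secondary.

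This rests on reading the sub-bullet's condition as operative and on the event being recorded as a clinical diagnosis. No event rates are given, so the number of participants affected cannot be computed, and nothing in the documents shows that either arm's safety results would be distorted. It should be corrected because a mandatory permanent-stop rule gives an inconsistent result and the correction is inexpensive. No view is taken on which clinical rule is right.

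**What to change.** The sponsor should reconcile three sentences: the Grade 3 endocrinopathy sub-bullet in Protocol 8.1.1, the Grade 4 endocrinopathy exception in the same section, and the endocrinopathy restart sentence in 7.4.4. Any difference between grades that is intended should be stated as such. Which conditions apply at each grade is for the sponsor's clinical team.

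The cost is a wording change to three sentences in the next protocol revision, or in an administrative letter if the sponsor judges it to be clarification only. It needs no new data or procedures.
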